Study Title: A Pharmacist Intervention for Monitoring and Treating Hypertension Using Bidirectional Texting

Version Number/Amendment	Approval Date
Original Protocol, Version 1.0	8/3/2019
Revised Protocol, Version 2.0	11/27/2019
Revised Protocol, Version 3.0	12/30/2019
Revised Protocol, Version 4.0	7/17/2020
Revised Protocol, Version 5.0	9/21/2020

Protocol Synopsis

Protocol Title	A Pharmacist Intervention for Monitoring and Treating Hypertension Using Bidirectional Texting
Main Criteria for Inclusion	Clinic measured blood pressure of ≥ 145 mmHg or ≥ 95 mmHg at two previous clinic visits or one previous clinic visit and on the day of enrollment. Previous clinic visit BPs must be within the past 18 months and measured at least 2 weeks apart from each other.
Study Objective	To evaluate whether our scalable SMS approach combined with a pharmacist-based intervention improves BP management and that is cost effective.
Study Design	A single-site, two-arm, single-blind randomized trial
Number of Sites	1 site, 3-4 clinic locations
Study Arms	2 Study Arms a) Intervention Group- Text 7 morning and 7 evening BP values at baseline. Monitored by a study pharmacist for 12 months. Research visits at 6 and 12 months b) Control Group- Text 7 morning and 7 evening BP values at baseline. Research visits at 6 and 12 months
Total Number of Subjects	420
Duration of Study Participation	12 months
Primary Outcomes	Mean difference in systolic blood pressure between the control and intervention groups at 12 months.
Secondary Outcomes	Mean difference in diastolic blood pressure between the control and intervention groups at 12 months. Total number of medication changes (i.e., dose, discontinuation, initiation, etc.) from baseline to 12 months.

	Total cost of medications, time spent by research staff, and clinic visits per patient from baseline to 12 months.
Statistical Design and Power	
The analysis will be done on an intent-to-treat basis regardless of the number of reported BP readings or the number of pharmacist interactions with the participant.
 
Our primary outcome will be a comparison of mean SBP values at 12 months. We will use a linear mixed effects model with mean BP at 12 months as the outcome. We will use random effects for clinic and physician nested within clinic to account for practice heterogeneity between clinics and providers.
 
Based on prior work with the CAPTION trial, we expect a mean decrease in SBP of 17.3 (SD = 17.7) mmHg in the intervention arm and a decrease of 11.6 (SD = 18.2) mmHg in the control arm. We expect a difference of 5.65 mmHg between the groups with an expected pooled standard deviation of 17.9 with equal sized groups. In order to have 85% power to detect a difference of 5.7 mmHg or larger decrease in SBP with a Type I error rate of 5% and a standard deviation of 17.9 mmHg, we would need 180 subjects per arm or 360 subjects total.
 
In preliminary work in the CAPTION trial, 13.4% of control subjects dropped out or were lost to follow-up. 14.0% of subjects dropped out of the intervention arm during the first 9 months. In order to retain power after reasonable attrition rates over 12 months, we will recruit an additional 14% in each group to ensure we have at least 85% power. In addition, the sample size should slightly increase to accommodate the interim analyses. This increases our total sample size to 420.
 
One interim analysis is planned after outcome data is received and the results are reported to the Data Safety and Monitoring Board from the first half of the study. The interim monitoring method of Lan and DeMets will be used with O'Brien-Fleming alpha spending function for the interim analyses. Accordingly, type I error rate of 0.00305 for the interim analysis and 0.4695 will be used for the final analyses. The current sample size of 420 patients total accommodates the interim analyses.

Futility Analysis	To be determined by the Data and Safety Monitoring Board

Table of Contents

Study Protocol.....	1
Protocol Approval Page	2
Protocol Version and Amendment Tracking	3
Protocol Synopsis	4
Table of Contents.....	6
Table of Appendices	7
Abbreviations	8
1. Introduction.....	9
1.1 Background.....	9
1.2 Clinical Experience with the Study Intervention	9
2. Objectives, Aims, and Hypotheses	10
2.1 Objective.....	10
2.2 Aims and Hypotheses	10

1.1 Background

Hypertension causes an estimated 395,000 deaths in the US each year: one out of every six deaths. Hypertension is second only to smoking as a modifiable cause of death in the US. Poor blood pressure (BP) control increases the risk of myocardial infarction, stroke and death and is often due to delays in treatment intensification. In our prior work, we demonstrated that a physician-pharmacist collaborative intervention with pharmacists embedded within the medical offices reduced BP and it was cost effective. However, pharmacists spent a considerable proportion of their time obtaining and aggregating patients' home BP measurements. Thus, we have developed a telehealth service called Centralized Healthcare Solutions that has successfully delivered clinical pharmacy services remotely to private physician offices, especially in small medical offices and rural locations. We have also developed an additional mhealth solution called What's your BP? (WyBP), a custom-built bi-directional SMS based (short message service, or texting) platform. WyBP is inexpensive (i.e., does not require investment in smartphone technology, or WiFi), acceptable to a broad range of patients (including the elderly and rural populations), scalable to subject volume observed in busy clinical settings, and easily integrated into typical clinic workflows. In two pilot studies, we demonstrated a high rate of adherence, indicating that patients were willing and able to take home BP measurements and send them to our research team.

This proposal combines our two prior efforts to use remotely located pharmacists and bi-directional texting to improve efficiencies, reduce cost and improve access to a dedicated pharmacist. A major gap in our knowledge is whether the potency of a "virtual" team member can be improved by home BP monitoring with technological support, especially in small medical offices that are unable to employ clinical pharmacists. The goal of this proposal is to evaluate whether our scalable SMS approach combined with a pharmacist-based intervention improves BP management cost effectively. To achieve this objective, we will determine if our intervention leads to decreases in BP; determine if our intervention leads to intensification of therapy; and determine the cost effectiveness of the intervention. At the end of this project, we expect to provide a novel, scalable and cost-effective approach for treating hypertension in rural populations by expanding the feasibility, scalability and dissemination of the Centralized Healthcare Solutions intervention. The intervention has important public health relevance: if this intervention could be implemented broadly in primary care practices and lead to a decrease of 5 mmHg BP, heart-disease deaths could be reduced by 15-20% and stroke deaths by 20-30%.

2.1 Objective

The objective of this study is to evaluate whether our scalable SMS approach combined with a pharmacist-based intervention improves BP management and that it is cost effective.

2.2 Aims and Hypotheses

2.2.1 Aim 1: Determine if our intervention leads to decreases in BP.

2.2.1.1 Hypothesis: Mean systolic BP in the pharmacist-intervention group will be significantly lower than mean systolic BP in the control group at 6 and 12 months.

2.2.1.2 Hypothesis: Mean diastolic BP in the pharmacist-intervention group will be significantly lower than mean diastolic BP in the control group at 6 and 12 months.

2.2.2 Aim 2: Determine if our intervention leads to intensification of therapy.

2.2.2.1 Hypothesis: Participants in the pharmacist-intervention group will have more treatment changes, on average, than those in the control group.

2.2.3 Aim 3: Determine the cost effectiveness of the intervention.

2.2.3.1 Hypothesis: The intervention will be cost effective when compared to the control group.

3. Subject Inclusion/Exclusion Criteria

3.1 Inclusion Criteria

- English or Spanish speaking males and females.
- 21 – 100 years of age.

- Clinic measured blood pressure of ≥ 145 mmHg or ≥ 95 mmHg at two previous clinic visits or one previous clinic visit and on the day of enrollment. Previous clinic visit BPs must be within the past 18 months and measured at least 2 weeks apart from each other.
- Lives in a zip code that is scored as a 4-10 on the Rural-Urban Commuting Area (RUCA) Codes.

3.2 Exclusion Criteria

- Currently pregnant or planning to become pregnant in the next year.
- Upper arm circumference over 50 cm (20 in)
- Prisoner status.
- Unable to provide own informed consent.

4. Study Design

4.1 Overview

The PharmText BP study was funded in September 2019 by the National Heart, Lung, and Blood Institute (NHLBI) of the National Institutes of Health (NIH). The study is being led by University of Iowa co-principal investigators [name], Associate Professor of Pharmacy Practice and Science and [name], [name] of Pharmacy Practice and Science and in the Department of Family Medicine.

The goal of PharmText BP is to conduct a study to evaluate whether our scalable SMS approach combined with a pharmacist-based intervention will improve BP management and that it will be cost effective. The entire study will last 5 years and involve recruitment of 420 participants from 3-4 clinics within 35 miles of University of Iowa Hospitals and Clinics. Participating clinics are listed in Appendix 1. All participants will live in areas that are considered rural by Rural-Urban Commuting Area Codes. The study aims to enroll at least 125 participants (30%) who represent minority populations.

All participants will have an initial screening/enrollment/baseline visit, a 2nd visit at 6 months, and a final visit at 12 months with a research intern. Each in-person visit will include research blood pressure measurements (Omron HEM 907-XL), interviews, and medical record review. In addition to the in-person visits, all participants will be provided with a home BP cuff (Omron 5 Series), enrolled in our bi-directional text-messaging platform, WyBP, and asked to submit 7 morning and 7 evening BP measurements via text message following the baseline visit. Text message prompts asking for these BP measurements will stop after the 14 measurements have been submitted, or after 15 days, whichever occurs first. Following the home BP measurements, participants will be randomized to either the pharmacist intervention arm or the texting-only control arm using a randomized block design with random block sizes with stratification according to clinic.

A timeline for the study procedures is provided in Appendix 2.

Key personnel roles for the study are described below:

Key Personnel	
Research Interns	3-5 full time staff members employed by Internal Medicine at UIHC who will recruit participants and collect data.
Research Pharmacists	2-3 clinical pharmacists will provide the intervention and at least 2 are certified hypertension clinicians as designated by the American Society of Hypertension. Pharmacists will provide telephone, text message, and email support for intervention participants and communicate with participant's doctors via the electronic medical record.

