4.4 Randomization and Treatment Arms

[name] created the stratified randomization lists for each clinic site. These lists are being uploaded to a website created by our software developer (unblinded). As participants have completed their home BP measurements, the research pharmacists will log into this website using a unique username and password. They will input the Record ID for the participant they need to randomize as well as the clinic location from which the participant enrolled. The website will inform the pharmacist of group assignment and they will record that in the Group Assignment REDCap form (Appendix 9). The website will store a log with a date and time stamp of which pharmacist randomized each participant to ensure that pharmacists do not intentionally or unintentionally alter the randomization in any way. This strategy should ensure that a relatively equal number of intervention and control participants are enrolled at each clinic.

4.4.1 Control Group:

Once the research pharmacist is informed of the participant's group assignment, they will contact the participants. The pharmacist will discuss their home BP measurements and only provide general education on hypertension. If the BP values remain elevated on home monitoring, the pharmacist will advise the participant to make an appointment with their physician to address BP elevations. This will be the only pharmacist contact for the control group.

4.4.2 Intervention Group:

The pharmacists will have access to the participants' electronic medical records, all information collected by the research interns, and the home BP values that are submitted via text message. Pharmacists will employ a patient-centered approach to improve participant's BP by providing support, education, and recommendations for treatment intensification, as necessary. They will communicate with participants via phone, text message, or email, based on participant preferences. They will not follow a specific protocol, but will base treatment decisions on current BP guidelines. They may schedule more home BP measurements than the 3 days per month. Recommendations to physicians will primarily be made through the electronic medical record to quickly improve BP control. They will also recommend laboratory testing if indicated (e.g., serum potassium or creatinine).

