The pharmacists will review the home BP values with the intervention subjects. If the home BP values are controlled, the pharmacist will continue to monitor home BP values.

However, if the pharmacist identifies issues such as poor medication adherence, inability to afford medications or other issues, they will work with the patient and physician to optimize therapy and/or reduce cost. If the pharmacist suspects white coat hypertension, they will make a recommendation to the physician to refer the patient to the University of Iowa ambulatory blood pressure service.

If BP values are elevated, the pharmacist will assess medication adherence, ability to pay for medications and whether the regimen is optimal to control BP based on patient demographics and co-existing conditions. The pharmacist will communicate recommendations for lifestyle and other changes directly to the subject. If medication changes are needed, the pharmacist will communicate to the physician through the electronic medical record. The pharmacist may recommend:

1. Increased dose of a medication.
2. Addition of a medication.
3. Discontinuation of a medication.
4. Modification of the regimen to optimize therapy, improve convenience (e.g. fixed-dose combinations) or reduce cost.

All participants in the pharmacist intervention group will continue to have access to a research pharmacist for the entire 12 months of follow up. Additionally, they will be asked to continue measuring and texting BP values (1 morning, 1 evening) for 3 days each month throughout the 12-month follow up.

The pharmacists will typically contact with the participants every 2 weeks while BP is not controlled. Once BP is controlled, they will continue monitoring the participant's records and home BPs and make contact at least every 2 months to support adherence and reassess BP control.

The REDCap forms that the pharmacists will use to record data are shown in Appendix 10

4.5 6-Month Visit Procedures

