Second, transition to control for patients who were uncontrolled at their baseline visit will be modeled using a generalized linear mixed effects model (GLMM) based on the Bernoulli distribution with a logistic link. We will test the intervention by including a fixed-effects term for the treatment assignment (intervention versus control). As before, we will include random effects for provider nested within clinic. Specifically, the model will be

$$\begin{aligned}
 \text{logit}(\mathbb{P}(Z_{cpio} = 1 | Z_{cpis} = 0)) &= \tau + \alpha_c + \gamma_{cp} + (\omega + \nu_c + \xi_{cp})X_{cpi}, \\
 (\alpha_c, \gamma_{cp})' &\stackrel{\text{iid}}{\sim} N(0, G_1), \\
 (\nu_c, \xi_{cp})' &\stackrel{\text{iid}}{\sim} N(0, G_2),
 \end{aligned}$$

where Z_{it} equals 1 if the i^{th} subject under the p^{th} provider within clinic c is controlled at time t , $t \in \{0, 6\}$, and zero otherwise.

Third, we will assess the duration of the change by modeling the odds of having controlled BP at 12 months among those uncontrolled at baseline but controlled at 6 months using a GLMM similar to that described above. All three models will contain any covariates (e.g., age, sex) that were not sufficiently addressed through randomization. In all analyses, the random effects incorporated into the final model will be chosen via Akaike Information Criterion with correction for small sample sizes (AICc).

Power: Based on prior work with the CAPTION trial, we expect a mean decrease in SBP of 17.3 (SD = 17.7) mmHg in the intervention arm and a decrease of 11.6 (SD = 18.2) mmHg in the control arm. We expect a difference of 5.65 mmHg between the groups with an expected pooled standard deviation of 17.9 with equal sized groups. In order to have 90% power to detect a difference of 5.7 mmHg or larger decrease in SBP with a Type I error rate of 5% and a standard deviation of 17.9 mmHg, we would need 180 subjects per arm or 360 subjects total.

In preliminary work in the CAPTION trial, 13.4% of control subjects dropped out or were lost to follow-up. 14.0% of subjects dropped out of the intervention arm during the first 9 months. In order to retain power after reasonable attrition rates over 12 months, we will recruit an additional 14% in each group to ensure we have at least 85% power. In addition, the sample size should be slightly increased to accommodate the interim analyses. This increases our total sample size to 420.

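### Home BP readings taken before randomisation are named in no Section 6 analysis; prespecifying mean run-in home SBP as a covariate would give a modest, nearly free gain in precision

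*Combined protocol and SAP*

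**What the plan says.** Section 4.1 has all participants "asked to submit 7 morning and 7 evening BP measurements via text message following the baseline visit". Prompts end once 14 values have arrived or after 15 days. The order is explicit: "Following the home BP measurements, participants will be randomized to either the pharmacist intervention arm or the texting-only control arm". Appendix 2 shows the same sequence for both arms.

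The readings have a role in both arms (Section 4.4). In the control arm: "If the BP values remain elevated on home monitoring, the pharmacist will advise the participant to make an appointment with their physician". In the intervention arm: "If the home BP values are controlled, the pharmacist will continue to monitor home BP values", while elevated values lead to a review of adherence, affordability and regimen. There is no fixed algorithm: "They will not follow a specific protocol, but will base treatment decisions on current BP guidelines".

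Entry rests on clinic values, "Clinic measured blood pressure of ≥ 145 mmHg or ≥ 95 mmHg at two previous clinic visits" or one such visit plus the enrolment day, with no home BP criterion. The primary outcome is SBP measured at the 12-month research visit.

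In Section 6 the primary mixed model has fixed effects for time and for arm by time, plus random effects for clinic and physician. The two models of BP control define control status from study visits. The medication-change model has arm as its only fixed effect, and the cost analysis adjusts only if the groups differ. The one general covariate provision for Aim 1 is: "All three models will contain any covariates (e.g., age, sex) that were not sufficiently addressed through randomization". Home BP appears in none of these, and no home mean, minimum number of readings or home cut-off is defined.

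**The concern.** A prognostic variable measured before randomisation in both arms can be adjusted for without risk of bias from treatment. Here it is averaged over as many as 14 readings on different days, and home values are not themselves an entry criterion. It may therefore carry information about 12-month SBP beyond the single-visit research BP.

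The imbalance clause does not secure that benefit. Adjustment gains precision because a covariate predicts the outcome, whether or not the arms happen to differ on it. Selecting covariates by observed imbalance also leaves the choice open until the data are in, so a later home-BP-adjusted result could be read as chosen after the fact. What is at stake is a somewhat narrower interval for the primary contrast and a clear prior commitment to it. The validity of the planned comparison is not in question.

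**Working it through.** **1. The plan's own figure.** Inputs from the synopsis and Section 6: difference 5.7 mmHg, SD of the decrease 17.9 mmHg, type I error 5%, 180 per arm. Sidedness is not stated; I take two-sided.
- n per arm = 2 × (1.960 + 1.036)² × 17.9² / 5.7² ≈ 178 for 85% power (179 with the noncentral t), so 180 reproduces.
- Power at 180 per arm by noncentral t is 85.4%.
- The 90% printed in Section 6 would need 208 per arm, so I start from the synopsis's 85%.
- Enrolment: 360 / 0.86 = 419, in line with 420.

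**2. Gain from the unadjusted SD of change.** Let home SBP explain a further share R² of variance (assumption). The SD becomes 17.9 × √(1 − R²).

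| R² | SD | Power |
|---|---|---|
| 0 | 17.90 | 85.4% |
| 3% | 17.63 | 86.4% |
| 5% | 17.45 | 87.1% |
| 10% | 16.98 | 88.8% |

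This is the wrong starting point if baseline research SBP is also adjusted for, as it should be.

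**3. Gain beyond baseline research SBP.** As written, the primary model carries baseline BP on the outcome side with its own arm effect at time 0. With complete data its 12-month contrast is therefore not baseline-adjusted. Assume equal variances at baseline and 12 months and a correlation ρ between them (not in the documents; range 0.3 to 0.7). Then:
- SD of change = σ√(2(1 − ρ)) = 17.9;
- residual SD after baseline adjustment = σ√(1 − ρ²) = 17.9 × √((1 + ρ)/2).

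Home SBP then multiplies that residual SD by √(1 − R²).

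| ρ | Residual SD | Power, baseline only | + 3% | + 5% | + 10% |
|---|---|---|---|---|---|
| 0.3 | 14.43 | 96.22% | 96.67% | 96.95% | 97.61% |
| 0.5 | 15.50 | 93.56% | 94.21% | 94.62% | 95.61% |
| 0.7 | 16.50 | 90.45% | 91.28% | 91.82% | 93.12% |

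The smallest gain is 96.67 − 96.22 = 0.45 points and the largest is 93.12 − 90.45 = 2.67 points: about 0.5 to 2.7.

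**4. The same gain as sample size and interval width.** Equivalent extra completers = 360 × R²/(1 − R²) = 11, 19 and 40 for 3%, 5% and 10%. The interval narrows by 1 − √(1 − R²) = 1.5%, 2.5% and 5.1%.

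**5. What a home-SBP-by-arm estimate could show.** For a continuous term per SD of home SBP with 360 completers, SE = 17.9 × √(2/180) = 1.89, and the 95% half-width is 1.96 × 1.89 = 3.7 mmHg. For a split at controlled versus not controlled at home, with share f controlled (assumption), SE = 17.9 × √(4/360) / √(f(1 − f)). At f = 10%, 20% and 30% the half-widths are 12.3, 9.2 and 8.1 mmHg, and power to detect a 5.7 mmHg difference in effect is about 15%, 23% and 28%.

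**The case against.** The strongest reply is that this is an optional refinement: nothing in the plan is biased or contradictory. The power gain is small once baseline research SBP is used, every R² is assumed, and the list in the covariate clause is open-ended, so home BP could still be admitted. Nor are the readings quite free. They are self-texted, prompts stop at 15 days however few have arrived, and the intent-to-treat analysis keeps participants whatever number they sent, so a rule for sparse or missing values is needed.

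Most of this stands and sets the size of the point. It does not remove it, because admission through observed imbalance is a different thing from prespecified adjustment, and a missing-value rule takes one sentence.

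A reader might also infer four stronger things that the documents do not support.
- *That run-in home BP determines care.* Pharmacists follow no fixed protocol, also have the medical record, and in the intervention arm receive new home readings every month.
- *That participants controlled at home dilute the effect and leave the trial underpowered.* Under Section 4.4.2 they stay under monitoring with contact at least every two months, and adherence and cost problems are still acted on. The expected 5.65 mmHg comes from an earlier trial, and the documents do not say whether its participants included such people. If they did, any dilution is already in that figure.
- *That such dilution could not be seen.* The data exist in both arms and can be examined; the analysis is simply not prespecified.
- *That an interaction test would settle whether the intervention failed or was diluted.* Its power is too low for that.

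**Conclusion.** The point holds as a modest omission. Readings requested from everyone before randomisation, which help steer pharmacist contact in both arms, are named in no planned analysis, and the only route in depends on observed imbalance. Prespecifying the home mean would add about 0.5 to 2.7 power points beyond baseline research SBP. This assumes a further 3% to 10% of residual variance explained, a baseline-to-12-month correlation of 0.3 to 0.7, equal variances, and 180 completers per arm at two-sided 5%. None of the variance shares or correlations is in the documents. Under the same assumptions, adjusting for baseline research SBP yields more than home SBP adds to it. The plan's primary comparison is not invalidated, and no shortfall in power from participants controlled at home can be established from the text.

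**What to change.** In Section 6:
1. Define run-in home SBP as the mean of all readings sent before randomisation, with the same definition for home DBP.
2. Name it as a prespecified covariate in the primary SBP model, and home DBP in the DBP model. Let its effect differ by time so that it adjusts the 12-month contrast by its own 12-month association. Include it alongside adjustment for baseline research SBP (or DBP), whatever the observed balance.
3. For participants with no readings, impute a single value from baseline research BP and add a missing indicator. The values precede randomisation, so this does not depend on arm.
4. Optionally, report the continuous home-SBP-by-arm estimate at 12 months with its 95% interval, labelled as a descriptive secondary analysis of low power.

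The cost is a few sentences of SAP text, best added before unblinded outcome data are seen. No new data are needed. The small downside is handling sparse or missing self-texted readings.
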